10.1.3. Methods for Evaluation of Measurable Disease

All measurements should be taken and recorded in metric notation using a ruler or calipers. All baseline evaluations should be performed as closely as possible to the beginning of treatment and never more than 4 weeks before the beginning of the treatment.

The same method of assessment and the same technique should be used to characterize each identified and reported lesion at baseline and during follow-up. Imaging-based evaluation is preferred to evaluation by clinical examination unless the lesion(s) being followed cannot be imaged but are assessable by clinical exam.

Clinical lesions Clinical lesions will only be considered measurable when they are superficial (*e.g.*, skin nodules and palpable lymph nodes) and ≥ 10 mm diameter as assessed using calipers (*e.g.*, skin nodules). In the case of skin lesions, documentation by color photography, including a ruler to estimate the size of the lesion, is recommended.

Chest x-ray Lesions on chest x-ray are acceptable as measurable lesions when they are clearly defined and surrounded by aerated lung. However, CT is preferable.

Conventional CT and MRI This guideline has defined measurability of lesions on CT scan based on the assumption that CT slice thickness is 5 mm or less. If CT scans have slice thickness greater than 5 mm, the minimum size for a measurable lesion should be twice the slice thickness. MRI is also acceptable in certain situations (*e.g.* for body scans).

Use of MRI remains a complex issue. MRI has excellent contrast, spatial, and temporal resolution; however, there are many image acquisition variables involved in MRI, which greatly impact image quality, lesion conspicuity, and measurement. Furthermore, the availability of MRI is variable globally. As with CT, if an MRI is performed, the technical specifications of the scanning sequences used should be optimized for the evaluation of the type and site of disease. Furthermore, as with CT, the modality used at follow-up should be the same as was used at baseline and the lesions should be measured/assessed on the same pulse sequence. It is beyond the scope of the RECIST guidelines to prescribe specific MRI pulse sequence parameters for all scanners, body parts, and diseases. Ideally, the same type of scanner should be used and the image acquisition protocol should be followed as closely as possible to prior scans. Body scans should be performed with breath-hold scanning techniques, if possible.

PET-CT At present, the low dose or attenuation correction CT portion of a combined PET-CT is not always of optimal diagnostic CT quality for use with RECIST measurements. However, if the site can document that the CT performed as part of a PET-CT is of identical diagnostic quality to a diagnostic CT (with IV and oral contrast), then the CT portion of the PET-CT can be used for RECIST measurements and can be used interchangeably with conventional CT in accurately measuring cancer lesions over

time. Note, however, that the PET portion of the CT introduces additional data which may bias an investigator if it is not routinely or serially performed.

FDG-PET While FDG-PET response assessments need additional study, it is sometimes reasonable to incorporate the use of FDG-PET scanning to complement CT scanning in assessment of progression (particularly possible 'new' disease). New lesions on the basis of FDG-PET imaging can be identified according to the following algorithm:

- a. Negative FDG-PET at baseline, with a positive FDG-PET at follow-up is a sign of PD based on a new lesion.
- b. No FDG-PET at baseline and a positive FDG-PET at follow-up: If the positive FDG-PET at follow-up corresponds to a new site of disease confirmed by CT, this is PD. If the positive FDG-PET at follow-up is not confirmed as a new site of disease on CT, additional follow-up CT scans are needed to determine if there is truly progression occurring at that site (if so, the date of PD will be the date of the initial abnormal FDG-PET scan). If the positive FDG-PET at follow-up corresponds to a pre-existing site of disease on CT that is not progressing on the basis of the anatomic images, this is not PD.
- c. FDG-PET may be used to upgrade a response to a CR in a manner similar to a biopsy in cases where a residual radiographic abnormality is thought to represent fibrosis or scarring. The use of FDG-PET in this circumstance should be prospectively described in the protocol and supported by disease-specific medical literature for the indication. However, it must be acknowledged that both approaches may lead to false positive CR due to limitations of FDG-PET and biopsy resolution/sensitivity.

Note: A 'positive' FDG-PET scan lesion means one which is FDG avid with an uptake greater than twice that of the surrounding tissue on the attenuation corrected image.

10.1.4. Response Criteria

10.1.4.1. Evaluation of Target Lesions

Complete Response (CR): Disappearance of all target lesions. Any pathological lymph nodes (whether target or non-target) must have reduction in short axis to <10 mm.

Partial Response (PR): At least a 30% decrease in the sum of the diameters of target lesions, taking as reference the baseline sum diameters.

Progressive Disease (PD): At least a 20% increase in the sum of the diameters of target lesions, taking as reference the smallest sum on study (this includes the baseline sum if that is the smallest on study). In addition to the relative increase of 20%, the sum must also demonstrate an absolute increase of at least 5 mm. (Note: the appearance of one or more new lesions is also considered progressions).

Stable Disease (SD): Neither sufficient shrinkage to qualify for PR nor sufficient increase to qualify for PD, taking as reference the smallest sum diameters while on study.

10.1.4.2. Evaluation of Non-Target Lesions

Complete Response (CR): Disappearance of all non-target lesions and normalization of tumor marker level. All lymph nodes must be non-pathological in size (<10 mm short axis).

Note: If tumor markers are initially above the upper normal limit, they must normalize for a patient to be considered in complete clinical response.

Non-CR/Non-PD: Persistence of one or more non-target lesion(s) and/or maintenance of tumor marker level above the normal limits.

Progressive Disease (PD): Appearance of one or more new lesions and/or *unequivocal progression* of existing non-target lesions. *Unequivocal progression* should not normally trump target lesion status. It must be representative of overall disease status change, not a single lesion increase.

Although a clear progression of “non-target” lesions only is exceptional, the opinion of the treating physician should prevail in such circumstances, and the progression status should be confirmed at a later time by the review panel (or Principal Investigator).

10.1.4.3. Evaluation of Best Overall Response

The best overall response is the best response recorded from the start of the treatment until disease progression/recurrence (taking as reference for progressive disease the smallest measurements recorded since the treatment started). The patient's best response assignment will depend on the achievement of both measurement and confirmation criteria.

For Patients with Measurable Disease (*i.e.*, Target Disease)

| Target Lesions | Non-Target Lesions | New Lesions | Overall Response | Best Overall Response when Confirmation is Required* |
|----------------|--------------------|-------------|------------------|--|
| CR | CR | No | CR | ≥4 wks. Confirmation** |
| CR | Non-CR/Non-PD | No | PR | ≥4 wks. Confirmation** |
| CR | Not evaluated | No | PR | |

| | | | | |
|---|-----------------------------|-----------|----|--|
| PR | Non-CR/Non-PD/not evaluated | No | PR | |
| SD | Non-CR/Non-PD/not evaluated | No | SD | Documented at least once ≥ 4 wks. from baseline** |
| PD | Any | Yes or No | PD | no prior SD, PR or CR |
| Any | PD*** | Yes or No | PD | |
| Any | Any | Yes | PD | |
| 
* See RECIST 1.1 manuscript for further details on what is evidence of a new lesion.
 
** Only for non-randomized trials with response as primary endpoint.
 
*** In exceptional circumstances, unequivocal progression in non-target lesions may be accepted as disease progression.
 
Note: Patients with a global deterioration of health status requiring discontinuation of treatment without objective evidence of disease progression at that time should be reported as “symptomatic deterioration.” Every effort should be made to document the objective progression even after discontinuation of treatment.
 | | | | |

11. CORRELATIVES AND BIOMARKER STUDIES

We will prospectively collect blood and tumor tissue specimens to determine biomarkers of response to treatment with ibrutinib in combination with cetuximab. Depending on tissue availability, not all studies may be able to be performed on every specimen.

Planned analyses include:

- Investigate ITK/BTK occupancy in tumor tissue to demonstrate potential therapeutic mechanisms of the combination therapy.
- Multiplex IHC to study the immune microenvironment
- BCR and TCR deep sequencing to identify dominant clone in peripheral blood. This work will be performed by Adaptive Biotechnologies
- Whole exome sequencing, RNAseq/gene expression profiling on baseline tissue to study quantitative evaluation of gene expression patterns and genomic alterations to demonstrate immune checkpoint targets, functional T cell responses, candidate tumor antigens

Analysis will be performed at University of California San Diego. Specimens should be sent to:

[name].

Biorepository Manager,

University of California San Diego, Moores Cancer Center

[name]
[name]
[name]
Office: [contact]
[contact]

Please refer to standard operating procedures for details on assays.

12. STATISTICAL METHODS AND ANALYSIS

12.1. Subject Information

Demographic data (age, sex, ethnicity, height, body weight) and baseline disease characteristics will be tabulated and summarized and presented in data listings.

12.2. Endpoints

12.2.1. Primary Endpoints

The primary endpoint is the clinical efficacy as defined by the overall response rate (proportion of patients with a partial or complete response in tumor burden based on best overall response) using RECIST v1.1.

12.2.2. Secondary Endpoints

Progression-free survival (PFS), defined as the interval from the date of first dose of study drug (ibrutinib or cetuximab whichever occurs first) to disease progression or death from any cause, whichever occurs first.

Overall survival (OS), defined as the date of first dose of ibrutinib or cetuximab, whichever given first, to the date of death from any cause.

Duration of response is measured from the time measurement criteria are met for complete response or partial response (whichever is recorded first) until the first date that recurrent or progressive disease is objectively documented (taking as reference for progressive disease the smallest measurements recorded since the treatment started) or death of any cause.

Overall frequency and severity of adverse events per CTCAE v4.0.

12.2.3. Exploratory Endpoints

Measurement of biomarkers of ibrutinib and cetuximab response, including BCR and TCR sequencing, immune checkpoint expression, cytokine profiling, gene expression profiling, tumor whole exome sequencing and neoantigen discovery, and to correlate biomarkers to clinical responses

12.3. Sample Size Determination and Primary Analysis

The primary analysis will use Simon's two stage minimax design. The one-sided overall Type I error rate will be 5%. The analysis population will be all subjects who have received at least one dose of study drug.

For the study treatment of ibrutinib plus cetuximab, the null hypothesis that the true response rate is 10% will be tested against a one-sided alternative of greater than 10%. 10% is chosen as the appropriate null response rate because based on historical data for single agent cetuximab in this population (Seiwert TY et al, 2014). In the first stage, 12 patients will be accrued, and enrollment will suspend pending outcome of the interim analysis. If there are 1 or fewer responses observed in these 12 patients at the interim analysis, this study will be discontinued for lack of efficacy. Otherwise, 6 additional patients will be accrued for a total of 18 patients. The null hypothesis will be rejected if 5 or more responses are observed among these 18 patients at the final analysis. The conclusion will be that the response rate is significantly greater than 10%. This study yields a one-sided Type I error rate of 5%, and under the assumption that all patients are followed until progression so that all best responses are observed, a power of 90% when the observed response is 40%. Under this design, if the null hypothesis is true, the probability of stopping the trial early will be 66%. Modification of these operating characteristics because of potential censoring of observations at the interim analysis is discussed below. We anticipate that one-sided Type I error will remain at 5% or less, and that true power will be between 80% and 90%, and that the probability of early stopping under the null will be at least 66%.

An initial version of this protocol included an ibrutinib plus nivolumab arm; based on emerging data, enrollment to that arm was halted. Patients treated with the ibrutinib/nivolumab combination will not count towards the 18 patients in the final analysis of the ibrutinib/cetuximab arm; results for patients treated with ibrutinib/nivolumab will be based on descriptive statistics only.

The Final efficacy analyses will calculate the uniformly minimum variance unbiased estimator (UMVUE), p-value and 95% CI for the response rates (Jung 2004, Koyama 2008). The calculation will be performed using R *clinfun* package (www.r-project.org).

12.4. Interim Analysis and Futility Stopping Rules

Enrollment will suspend after stage 1 enrollment is complete, until the results of the interim analysis are known. The interim analysis will be conducted when 12th subject has reached the 8 week restaging visit. As described above, if there are 1 or fewer responses observed among the first 12 patients, this study will be discontinued for lack of efficacy. Note that at this time point, some subjects may not yet have attained their best response. This will reduce the chance of observing a response, and the power will be decreased by an amount which is estimated below. The final power is estimated at 80% for this study. If the null hypothesis is true and the true response rate is 10% or less, the probability of stopping the trial early will be 66%.

Brahmer reports single agent use of nivolumab in squamous cell lung cancer, which is biologically very similar to HNSCC. In this paper, time to first response is given in Figure 2, panel A, (Brahmer J et al, 2015). We use these data to estimate the operating characteristics of the Simon design, adjusting for potential censoring of response at the interim analysis. In Table 1 below, column 2 shows the time on study for each subject at the interim analysis, assuming accrual of 2 subjects per month. Column 3 shows the proportion of responses which were observed by that time in Brahmer 2015.

| Table 1. Time on study for the first 12 patients at the interim analysis, given accrual of 2 subjects per month. | | |
|--|---|--|
| Patient start month | Time on study, when the last enrolled patient has been observed for 8 weeks | Proportion of responses observed by this time. (Figure 2, panel A, Brahmer 2015) |
| Patient 1 & 2 start at month 1 | 28w | 89% |
| Patient 3 & 4 start at month 2 | 24w | 89% |
| Patient 5 & 6 start at month 3 | 20w | 85% |
| Patient 7 & 8 start at month 4 | 16w | 63% |
| Patient 9 & 10 start at month 5 | 12w | 59% |
| Patient 11 & 12 start at month 6 | 8w | 59% |

From the average of the third column of the above table, we obtain a mean observed response rate of 74% of the true response rate, where the true response rate assumes we observed all these subjects to progression. Then, for this study, using a true response rate of 10% as the original null hypothesis, the observed null response rate will be 74%*10%, which is 7.4%. This adjustment accounts for the censoring from assessing response at an early time point. Similarly, the unadjusted alternative hypothesis is that the response rate equals 40%, and the adjusted

alternative hypothesis is the response rate equals $74\% \times 40\%$, which is 30%. The probability of early stopping ($p(x \leq 1), x \sim \text{Bin}(n=12, p=0.30)$) under the adjusted alternative hypothesis is 9%. The probability of stopping early ($p(x \leq 1), x \sim \text{Bin}(n=12, p=0.4)$) under the original alternative hypothesis is 2%. To compute the power under the adjusted alternative hypothesis, note that the probability that we reject the null is $p(\text{reject at stage II} \mid \text{continue at stage I}) \times p(\text{continue at stage I})$. We can adjust the second factor, $p(\text{continue at stage I})$, by multiplying the power computed with the unadjusted alternative by the ratio: probability of continuing under adjusted alternative hypothesis ($1 - 9\% = 91\%$) divided by probability of continuing under unadjusted alternative hypothesis ($1 - 2\% = 98\%$), which is 0.93. Thus, this design using an interim analysis at week 8 for subject 12 will actually yield a power of 0.9×0.93 , which is 0.84, when the true response rate is 0.4 and the adjusted response rate is 0.4×0.74 .

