| Statistical Methods and Data Analysis: | 
All efficacy and safety analyses will be performed among all patients who received at least one dose of study medication.
 
Primary Efficacy Analysis:
 
Demographic and clinical characteristics of the patients will be summarized using frequency counts and percentages, means and standard deviations or medians and interquartile ranges, as appropriate. Best overall response will be summarized as proportion with 95% confidence intervals.
 |

| | |
|----------------------------------|--|
| | 
Secondary Efficacy Analysis:
 
Progression-free survival, overall survival, and duration of response will be described by Kaplan-Meier models to plot these endpoints and estimate median times with a 95% confidence interval.
 
Exploratory Efficacy Analysis:
 
Serial estimate of biomarker expression will be plotted and summarized over time using means and standard deviations, possibly on a log scale.
 
Safety Analysis:
 
Adverse events will be summarized by grade, type and patient.
 
The initial protocol had an ibrutinib/nivolumab arm; this was closed due to emerging scientific data. Several patients were treated on this arm prior to closure; results from the patients treated with this combination will be described by descriptive statistics.
 |
| Interim Analysis | 
The interim analysis will be conducted when the 12th patient has been on study for 8 weeks. 12 patients will be accrued to receive ibrutinib and cetuximab and enrollment will suspend pending outcome of the interim analysis. If there are 1 or fewer responses observed in these 12 patients at the interim analysis, this study will be discontinued. If the null hypothesis is true and the true response rate is 10% or less, the probability of stopping the trial early will be 66%.
 
Safety will be continuously monitored.
 |
| Sample Size Determination | 
Based on Simon's two stage minmax design, 18 patients treated with ibrutinib/cetuximab will yield a study with 84% power at one-sided type I error rate of 0.05 to detect a true response rate of greater than 40% , versus a null hypothesis of 10%. These power estimates adjust for potential censoring of observations at the end of Stage 1 (at the interim analysis; please see statistical section for explanation). The initial protocol had an ibrutinib/nivolumab arm; this was closed due to emerging scientific data.
 |

Abbreviations

| | |

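### Section 12.4 states a censoring-adjusted power of 80% where its own calculation gives 84%, and the flat 66% early-stopping figure for the 8-week interim is about 78% under the plan's own adjustment

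*Combined protocol and SAP*

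**What the plan says.** Section 12.3 sets the design: "The primary analysis will use Simon's two stage minimax design", with a null response rate of 10% and power evaluated at 40%. Twelve patients enter stage 1, and the study stops if 1 or fewer respond. Otherwise 6 more are enrolled, and the null is rejected with 5 or more responses among 18. With every best response observed, the section gives 90% power, 66% early stopping under the null and a Type I error of 5%. It then says these values will shift because of censoring at the interim: "We anticipate that one-sided Type I error will remain at 5% or less, and that true power will be between 80% and 90"%, with early stopping under the null of at least 66%.

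Section 12.4 places the interim at the 12th patient's 8-week restaging and accepts that some responses will not yet be visible. It announces an estimate to follow, then says "The final power is estimated at 80% for this study" and, for the null, "the probability of stopping the trial early will be 66"%. From its Table 1 of visibility by time on study, "we obtain a mean observed response rate of 74% of the true response rate". That turns 10% into 7.4% and 40% into 30%, and the section finishes with a power of 0.84.

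The synopsis says 18 patients "will yield a study with 84% power at one-sided type I error rate of 0.05" and describes that power as adjusted for censoring. The synopsis and Section 12.8 repeat the flat 66%.

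**The concern.** The 80% and the 84% are both offered as power after the same allowance for unseen responses, so they cannot both be right. The 66% is attached to the 8-week interim in three places, yet Section 12.4 derives a lower null rate for exactly that interim and never carries it into the stopping probability. In the synopsis the power is adjusted and the early-stopping figure is not.

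These are the numbers from which an ethics committee or monitoring board learns what the futility rule does. As written, they understate how often the interim will end the trial when the regimen is inactive, and they leave the adjusted power ambiguous by 4 points.

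**Working it through.** **Inputs.** From Section 12.3: n1 = 12, stop if X1 ≤ 1; n = 18, reject if total responses ≥ 5; null 10%. From Section 12.4: alternative 40%; visibility at the interim of 89, 89, 85, 63, 59 and 59% for successive pairs of patients. Their mean is 444/6 = 74.0%, which reproduces.

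**1. Uncensored design.** With X1 ~ Bin(12, p) and X2 ~ Bin(6, p):
- P(stop) = P(X1 ≤ 1). At 10%: 0.2824 + 0.3766 = 0.659. The 66% reproduces.
- P(reject) = Σ P(X1 = x) · P(X2 ≥ 5 − x), for x = 2 to 12. At 40%: 0.903. The 90% reproduces.
- The same sum at 10% is 0.0277, the attained one-sided Type I error.
- A search over all two-stage designs with Type I error ≤ 0.05 and power ≥ 0.90 for 10% versus 40% returns this minimax design: 1/12, then 4/18 as the largest count that does not reject.

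**2. The plan's power adjustment.** Section 12.4 multiplies the uncensored power by the ratio of continuation probabilities:
- P(X1 ≤ 1) at 30% = 0.085, which the plan rounds to 9%.
- P(X1 ≤ 1) at 40% = 0.020, which the plan rounds to 2%.
- 0.9 × (1 − 0.085)/(1 − 0.020) = 0.84. With the plan's rounding, 0.9 × 0.93 = 0.837.

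So 84% reproduces and 80% does not. Other routes tried do not give 80% either: applying 30% to both stages gives 0.66, and 59% visibility for all 12 patients gives 0.75 by the ratio method or 0.77 exactly.

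**3. Exact joint calculation.** Let each stage-1 response be visible at the interim with probability 0.74, independently, and count every best response at the final analysis.
- Power at 40%: 0.854. With the Table 1 values patient by patient: 0.856.
- Type I error at 10%: 0.024.

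The ratio method comes out slightly lower because it holds P(reject | continue) fixed. That probability is 0.903/0.980 = 0.921 without censoring and 0.854/0.910 = 0.939 with it.

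**4. Early stopping under the null with the plan's adjusted rate.** P(X1 ≤ 1) for Bin(12, 0.074) = 0.3975 + 0.3812 = 0.779. The patient-by-patient version is also 0.779.

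| Quantity | Stated for the 8-week interim design | All responses observed | Plan's 74% visibility |
|---|---|---|---|
| Early stopping at 10% | 66% | 65.9% | 77.9% |
| Power at 40% | 80% and 84% | 90.3% | 84.0% (ratio), 85.4–85.6% (exact) |
| Type I error at 10% | 5% | 2.8% | 2.4% |

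**5. Sensitivity of exact power at 40%.** If visibility is 59% for all 12 patients, power is 77%. If it is 89% for all 12, power is 89%.

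**The case against.** The strongest reply is that little here misleads. Section 12.3 warns that the figures will be modified, gives a power range that contains 80, 84 and 85%, and says early stopping will be at least 66%. Extra stopping under the null only ends an inactive regimen sooner. At the design alternative, Section 12.4 openly reports the rise in early stopping from 2% to 9%. Much of this stands: the plan is candid that censoring matters. But a range in one section does not reconcile two point values in another, and the three statements about the interim give 66% without the bound.

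Several stronger readings are tempting, and the documents do not support them:
- *Three conflicting power figures.* The 90% is explicitly conditional on follow-up to progression and reproduces on that condition. Only 80% against 84% conflicts.
- *A wrong Type I error.* "This study yields a one-sided Type I error rate of 5"% is loose wording for an attained 2.8%, but 5% is the design limit ("The one-sided overall Type I error rate will be 5"%), it is met, and the same section also says 5% or less. The difference is conservative.
- *An invalid power method.* The ratio method is about 1.5 points low. No decision turns on that.
- *An undisclosed source for the visibility figures.* Section 12.4 says they come from single-agent nivolumab in squamous lung cancer and gives its reason. The documents contain no time-to-response data for cetuximab, so the size of any mismatch cannot be shown.
- *More stopping of a moderately active regimen than stated.* The plan states no early-stopping probability for a true rate between 10% and 40%, so no stated value is exceeded.

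**Conclusion.** Two figures need correcting. The adjusted power of 80% in Section 12.4 is 4 points below the plan's own 84%, and about 5 points below the exact value of roughly 85%. The flat 66% early stopping in the synopsis, Section 12.4 and Section 12.8 is about 12 points below the 78% that follows from the plan's 7.4%.

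Both corrected values rest on the plan's assumptions: accrual of 2 patients per month, the Table 1 visibility figures, and a true rate of exactly 10% or 40%. The exact power also assumes that responses unseen at the interim are counted at the final analysis. For a true rate below 10%, early stopping is higher still, so even without censoring 66% would be a lower bound.

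A reader might infer that the design itself is faulty. It is not: the minimax design, the cut-offs of 1 of 12 and 5 of 18, and the sample size are confirmed and need no change.

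**What to change.** - **Section 12.4, power:** replace 80% with the derived 84%. Alternatively, adopt the exact 85% in place of the ratio method and update the end of Section 12.4 and the synopsis to match.
- **Synopsis, Sections 12.4 and 12.8, early stopping:** state that under a true 10% rate it is 66% if all responses were observed and about 78% with interim censoring.
- **Section 12.3, Type I error:** print the attained one-sided value (2.8% uncensored, 2.4% with censoring) beside the 5% limit.
- **Optional:** show how power at a true 40% depends on visibility, from about 77% (59% visible for all 12 patients) to 89% (89% visible for all 12).

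The cost is text only. The visible consequence is that early stopping under the null is reported as higher than it is now.
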